6.8.4 Other Health Assessments

PHQ-9 & GAD-7

- Brief and validated measures of the presence and severity of depression and generalised anxiety, respectively.⁴²
- PHQ-9 is a brief, self-administered, screening questionnaire for depression, which scores each of the nine DSM-V major depression criteria as '0' (not at all) to '3' (nearly every day). It can be used to make a tentative diagnosis of depression in at-risk populations (e.g. those with coronary heart disease or after stroke), whereby participants who score ≥ 10 are likely to have clinically significant depression.
 - In this study, the PHQ-9 will be used as a continuous measure to monitor the severity of depression and response to treatment.
 - If a participant has scored >10 on Q9 of the PHQ-9, or positively responded to the final question 9 'thoughts that you would be better off dead, or of hurting yourself in some way', a member of the study team will advise them to see their GP (or alternate health care professional as applies in the local context) and a letter will be sent to the treating doctor informing them of the result.
- GAD-7 is a valid and efficient, brief tool for screening for generalised anxiety disorder and assessing its severity in clinical practice and research.⁴³ A score of ≥ 10 represents a reasonable cut point for identifying cases of generalised anxiety. Cut points of 5, 10, and 15 might be interpreted as representing mild, moderate, and severe levels of anxiety GAD-7.

PSQI

- Designed to assesses overall sleep quality in clinical populations, covering 19 self-reported items across seven sub-categories: subjective sleep quality, sleep latency, sleep duration, habitual sleep efficiency, sleep disturbances, use of sleeping medication, and daytime dysfunction;⁴⁴ with five additional questions rated by the respondent's roommate or bed partner, if available.
- Administration by self-report and it generally takes 5-10 mins to complete. Scores >5 are generally indicative of poor sleep quality. In this study, the PSQI will be analysed as a continuous measure.

EQ-5D-5L

- Measures HRQoL across five dimensions (mobility, self-care, usual activities, pain/discomfort, and anxiety/depression), each rated according to five levels, as well as providing an integrated utility score for calculating an overall score against population-based preference weights.

Mobility & Sleep

- Participants will also be invited for the home application of actigraphs and a completion of a sleep diary to monitor their sleep-wake and activity patterns over 7-days in the next 2 weeks according to established protocols. These data will be analysed centrally to compute sleep efficiency, nocturnal awakenings, sleep timing, total sleep and activity time. The Sleep diary data are used to assist interpretation of actigraphy results in accordance with recommendations of the American Academy of Sleep Medicine. Actigraphy will also provide a measure of activity, as a proxy for physical activity. Both sleep and physical exercise may be important potential mediators of the primary outcome.

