6.6 Schedule of Evaluations

Table 1: Schedule of Evaluations

Visit Number	0	1	2	3	4	5
Time (Weeks [w]/Months [m])	-1m to 0	0	6w	6m	12m	18m
Window Period	-	-	±1w	±1m	±1m	±1m
Visit Type	Online + Phone	Clinic*	Phone	Clinic*	Phone	Clinic*
Remote / Electronic Informed Consent	X					
In-person Written Informed Consent		X				
SPHERE Questionnaire	X	X				
Blind MoCA	X					
Eligibility – Inclusion/Exclusion Criteria	X	X				
Medical History, Demographics & Socio-Economic Status		X				
Pregnancy Test – where required		X				
Lifestyle – Smoking, Diet, Alcohol		X		X		X
History of Health Service Use for COVID-19/Visits to Medical Professionals		X		X		X
Anthropometrics – Height & Weight		X				X
Blood Pressure, Heart Rate		X		X		X
Fasting Bloods	Haematology/Electrolytes/Renal/Liver Function – full blood count, Na, K, urea, nitrogen, creatinine, eGFR, ALT, AST, CK		X			X
	Glucose/Lipids/Inflammation – glucose, total cholesterol, LDL, HDL, triglycerides, CRP		X			X
	Neurodegenerative Biomarkers – 220 participants		X			X
Cognitive Assessments – SDMT, RAVLT-D, OTMT-A, OTMT-B, D-KEF-CWIT, SF		X		X		X
Health Assessments – PHQ-9, GAD-7, PSQI, EQ-5D-5L		X		X		X
Actigraphy plus Sleep Diary – 7-day Capture		X		X		X
Brain MRI – 220 participants		X				X
Dispense Study Medication – treatment arm only		X		X	X	
Study Medication Adherence & Accountability – treatment arm only			X	X	X	X
Concomitant Medications		X	X	X	X	X
SAEs/AESIs			X	X	X	X

*For participants who cannot attend the clinic, efforts will be made for visit assessments to be conducted remotely via tele-/videoconference.

ALT – Alanine Aminotransferase

AST – Aspartate Aminotransferase

CK – Creatine Kinase

CRP – C-Reactive Protein

D-KEF-CWIT – Delis-Kaplan Executive Functioning System “Stroop” Colour-Word Interference Test

GAD-7 – Generalised Anxiety Disorder-7

HDL – High-Density Lipoprotein

LDL – Low-Density Lipoprotein

MoCA – Montreal Cognitive Assessment

MRI – Magnetic Resonance Imaging

PSQI – Pittsburgh Sleep Quality Index

RAVLT-D – Rey Auditory Verbal Learning Test – Delayed Recall

SDMT – Symbol Digit Modalities Test

SF – Semantic Fluency

SPHERE – Somatic and Psychological Health Report

eGFR – estimated Glomerular Filtration Rate
EQ-5D-5L – EuroQoL 5-Dimensional 5- Level Questionnaire

OTMT – Oral Trail Making Tests A & B
PHQ-9 – Patient Health Questionnaire-9

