6.10 Communications with Health Care Providers

The study team will communicate with GPs or alternate designated health care provider (according to local context) via telephone, mail or email (if available), at least three times throughout the study.

1. Prior to participant participation. The study procedures will be briefly explained, including information about the study medication, and any concerns regarding participation will be sought.
 - If at the screening stage, a participant is ineligible for the study or a physical, mental or social health issue has been identified, the GP (or alternate health care provider) will also be advised particularly if further investigations or consultation with the participant may be required.
2. When the participant is randomised to the study.
3. At the end of the trial, regardless of whether the participants have dropped out or completed the trial, GP (or alternate health care providers) will be provided with their participants blood test results and interpreted neuropsychological test results.

7 Study Treatment & Adherence

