20.8 Appendix 8 – PHQ-9

PATIENT HEALTH QUESTIONNAIRE (PHQ-9)

NAME: _____ DATE: _____

Over the *last 2 weeks*, how often have you been bothered by any of the following problems?
(use “✓” to indicate your answer)

	Not at all	Several days	More than half the days	Nearly every day
1. Little interest or pleasure in doing things	0	1	2	3
2. Feeling down, depressed, or hopeless	0	1	2	3
3. Trouble falling or staying asleep, or sleeping too much	0	1	2	3
4. Feeling tired or having little energy	0	1	2	3
5. Poor appetite or overeating	0	1	2	3
6. Feeling bad about yourself — or that you are a failure or have let yourself or your family down	0	1	2	3
7. Trouble concentrating on things, such as reading the newspaper or watching television	0	1	2	3
8. Moving or speaking so slowly that other people could have noticed. Or the opposite — being so fidgety or restless that you have been moving around a lot more than usual	0	1	2	3
9. Thoughts that you would be better off dead, or of hurting yourself in some way	0	1	2	3

add columns: + +

TOTAL:

(Healthcare professional: For interpretation of TOTAL, please refer to accompanying scoring card.)

10. If you checked off *any* problems, how difficult have these problems made it for you to do your work, take care of things at home, or get along with other people?

Not difficult at all _____

Somewhat difficult _____

Very difficult _____

Extremely difficult _____

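### The PHQ-9 referral rule needs a score above 10 on an item that scores at most 3, so a high total with item 9 at zero triggers no referral under it

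*Protocol*

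**What the plan says.** Section 6.8.4 (PHQ-9 & GAD-7) describes the PHQ-9 as a questionnaire that "scores each of the nine DSM-V major depression criteria as '0' (not at all) to '3' (nearly every day"). It adds that participants scoring 10 or more "are likely to have clinically significant depression". It then gives the referral rule. A member of the study team advises the participant to see their GP (or local equivalent), and a letter goes to the treating doctor, in either of two cases:

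- "If a participant has scored >10 on Q9 of the PHQ-9"; or
- the participant responds positively to question 9.

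Appendix 8 (section 20.8) shows question 9 as one line of the form, "Thoughts that you would be better off dead, or of hurting yourself in some way", with the response columns 0, 1, 2 and 3. The form sums the nine items to a total.

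The schedule in section 6.6 lists "Health Assessments – PHQ-9, GAD-7, PSQI, EQ-5D-5L" at Visits 1, 3 and 5, that is, at baseline, 6 months and 18 months.

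Section 6.10 has a separate route to the GP. At the screening stage the GP is also advised if "a physical, mental or social health issue has been identified". At the end of the trial the GP receives "blood test results and interpreted neuropsychological test results".

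**The concern.** A threshold above 10 cannot apply to an item with a maximum of 3. The second trigger already covers item 9, so the first has a purpose only if it was meant for the total score. As written it does nothing, and it is the only numerical PHQ-9 referral threshold in the protocol.

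A participant whose total is at or above the protocol's own cut point for likely depression, but who answers not at all to item 9, therefore gets no GP advice and no letter under this rule. This could readily happen in the trial population. The Introduction names fatigue, disturbed sleep and anxiety or depression among the commonest long COVID symptoms. Section 6.8.1 admits participants on any positive SPHERE response, including its anxiety-depression arm. The PHQ-9 items on sleep, tiredness and concentration (items 3, 4 and 7) can contribute 3 × 3 = 9 points between them. Some high totals may reflect fatigue rather than depression, but the protocol applies its cut point without making that distinction.

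The issue is participant safety. Sample size, power and the primary analysis are not involved.

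**Working it through.** **Inputs**

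| Input | Value | Source |
|---|---|---|
| Score range of each item | 0 to 3 | Section 6.8.4; Appendix 8 |
| Number of items | 9 | Section 6.8.4; Appendix 8 |
| First trigger as written | above 10 on item 9 | Section 6.8.4 |
| Second trigger | positive response to item 9, i.e. 1, 2 or 3 | Section 6.8.4 |
| Cut point for likely depression | total of 10 or more | Section 6.8.4 |
| PHQ-9 visits | 1, 3 and 5 | Section 6.6 |

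**Step 1: can the first trigger be met?** Item 9 takes the values 0, 1, 2 or 3. None exceeds 10, so the first trigger is never met at any of the three visits. The rule is equivalent to item 9 ≥ 1.

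**Step 2: how high can the total go without a referral?** The maximum total is 9 × 3 = 27. With item 9 at zero, the other eight items give at most 8 × 3 = 24. A total of 25, 26 or 27 needs item 9 to be at least 25 − 24 = 1, so those totals are always referred through the second trigger.

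**Step 3: which scores are missed?** This depends on the intended rule. Both readings have item 9 = 0:

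- If a total above 10 was meant, the missed totals are 11 to 24, which is 24 − 11 + 1 = 14 values.
- If a total of 10 or more was meant, the missed totals are 10 to 24, which is 24 − 10 + 1 = 15 values.

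These counts show how much of the scale is left uncovered. They are not counts of participants. The protocol gives no PHQ-9 distribution, so an expected number cannot be derived.

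**Step 4: does another provision close the gap?**

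- Section 6.10 covers a mental health issue found at screening. It sets no PHQ-9 threshold and does not reach Visits 3 and 5, so two of the three PHQ-9 assessments lie outside it.
- The end-of-trial report to the GP in section 6.10 names blood and neuropsychological results, not the PHQ-9. Section 17.5 likewise mentions only neuropsychological scores.
- Section 13.2.2 does not list depression as an adverse event of special interest.
- The note on the Appendix 8 form about a scoring card concerns interpretation of the total, not referral.

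No section states a referral trigger on the PHQ-9 total.

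**The case against.** The strongest reply is that nobody would apply the sentence literally. Its second half names question 9 separately and quotes it, so the first half can sensibly mean only the total. The cut point of 10 stands in the same bullet, and the form itself produces a total for a clinician to interpret. On this view the sentence is a drafting slip whose repair is obvious, and no participant has been shown to be missed. Other contacts might also pick people up: section 6.10 sets three GP contacts as a minimum rather than a limit, and the telephone interviews in section 6.7 ask about ongoing health.

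Part of this stands. The wording is almost certainly a slip rather than a deliberate choice, the self-harm trigger works, and further GP contact is permitted. But permission to contact a GP is not a requirement to do so when the PHQ-9 is high. Staff who recognise the slip must still choose between above 10, as written, and 10 or more, as in the cut point. Sites in Australia and Chile could therefore treat a total of exactly 10 differently, or could apply only the trigger that works.

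It is also fair to say that the cut point of 10 or more is offered as a description of likely depression and not as a referral threshold. Choosing it over above 10 is therefore a decision for the sponsor.

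**Conclusion.** The concern holds. One of the two referral triggers cannot be met, and the rule as written refers only participants who respond positively to item 9. Under it, a total as high as 24 of 27 with item 9 at zero leads to no GP advice and no letter. At baseline, section 6.10 may catch some of these participants; at 6 and 18 months it does not apply.

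That the trigger cannot be met follows directly from the item range and needs no assumption. That participants would actually go without referral assumes staff follow the text as written, and how many is unknown. The sentence should be corrected because it is an operative safety threshold. It has no bearing on the trial's statistical conclusions.

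**What to change.** In section 6.8.4, reword the first trigger as a total PHQ-9 score of 10 or more, which agrees with the cut point in the same bullet. If the sponsor intends a total above 10, state that instead; the smallest edit is then to replace the reference to Q9 in that clause with the total score. Keep the positive response to question 9 as a separate trigger.

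The cost is one sentence in the protocol and possibly some additional GP letters.

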6.9 Sub-Study – Neurodegenerative Markers & MRI

The following assessments will occur in a subset of 220 participants. The assessments will take place at Visit 1 and Visit 5.

6.9.1 Neurodegenerative Markers

Bloods will be collected for measurement of apolipoprotein E, inflammatory and other neurodegenerative markers. The bloods will be collected after an overnight fast (>8 hours) and drawn at 08:00-11:00am according to standardised procedures. The blood will then be immediately centrifuged, and the plasma locally stored at -80°C within 2 hours of collection. The bloods will be shipped at the end of the study for subsequent storage and analysis on a SIMOA immunoanalyser at the Department of Neuroscience (Alfred Hospital Precinct), Monash University, Melbourne, Australia. Key markers of neurodegeneration to be measured include Ptau-181, neurofilament light chain (NfL) and A β 42/40, and DNA extraction for apolipoprotein E genotype. Peripheral markers of oxidative stress and inflammatory markers relevant to neurodegeneration (IL-6, IL-1 β , NAD⁺, TNF- α , hsCRP) will also be collected for subsequent exploratory analyses.

6.9.2 MRI Scanning

MRI scanning will be undertaken on 3-Tesla clinical scanners at the Alfred Hospital (Melbourne, Australia), Brain and Mind Centre (Sydney, Australia), and the Clínica Alemana (Santiago, Chile). Scan sessions will take approximately 45 minutes and will include acquisition of:

- whole brain 3D T1-weighted, T2-weighted, and fluid-attenuated inversion structural images;
- 2D diffusion-weighted microstructural images;
- 3D pseudo-continuous arterial spin labelling perfusion images;
- 3D susceptibility-weighted images; and
- magnetic resonance spectroscopy in the posterior cingulate.

All scans will be acquired with the participant at rest, with no requirements for contrast or other injections, breath holds or other active engagement. Participant screening and data acquisition will be performed by clinical radiographers at all sites. Following local acquisition, all scans will be securely transferred in DICOM format, and housed on the Monash University XNAT imaging informatics server, Melbourne, Australia.

According to standard procedures, where an abnormal finding is detected on the MRI scan that is deemed by the site radiologist to require clinical follow-up or monitoring (e.g. small cerebral aneurysm, plaque suspicious of multiple sclerosis, small meningioma), the participant will be notified and the report forwarded to the participant's primary care or other physician (i.e. in Australia, a general practitioner [GP]) unless a more urgent follow-up is necessary (e.g. primary or secondary tumour, cerebral aneurysm, arteriovenous malformation); in which case we arrange for a direct referral to a neurologist in addition to GP. In other countries, appropriate follow-up will be arranged in accordance with the local clinical pathways). Asymptomatic incidental findings (e.g. small spot-like abnormalities in the cerebral white matter) that are not deemed to have clinical relevance are not reported back to participant; because there is variability in what different radiologists will include in their report and it can cause a lot of anxiety for participants without any commensurate benefit.

6.10 Communications with Health Care Providers

The study team will communicate with GPs or alternate designated health care provider (according to local context) via telephone, mail or email (if available), at least three times throughout the study.

1. Prior to participant participation. The study procedures will be briefly explained, including information about the study medication, and any concerns regarding participation will be sought.
 - If at the screening stage, a participant is ineligible for the study or a physical, mental or social health issue has been identified, the GP (or alternate health care provider) will also be advised particularly if further investigations or consultation with the participant may be required.
2. When the participant is randomised to the study.
3. At the end of the trial, regardless of whether the participants have dropped out or completed the trial, GP (or alternate health care providers) will be provided with their participants blood test results and interpreted neuropsychological test results.

7 Study Treatment & Adherence

7.1 Study Treatment

Participants who meet the eligibility criteria will be randomised to receive standard care or 6-monthly supplies of atorvastatin 40mg on top of standard care for a period of 18 months.

7.2 Blinding

Study treatment is open-label. The randomisation allocation will be blinded to researchers conducting cognitive assessments and endpoint adjudicators. All participants, physicians and other study team members will be aware of participant treatment allocation. However, participants will only be informed of their allocation after all the baseline assessments have been completed in order to reduce the risk of differential withdrawal between the two arms.

7.3 Treatment Adherence

To maximise participant adherence to study medication, the following procedures will be implemented:

- Participant education on the importance of taking study medication, including timing, storage, and what to do in the event of a missed dose;
- Returned tablets will be counted and recorded by the study team;
- Participants will be provided with contact details of the responsible researcher so that they can make contact if for any reason they are unable to continue their study medication or have missed multiple doses and are unsure whether to continue.

7.4 Management of Possible Treatment Related Side-Effects

The following strategies (Table 2) can be employed for participants with side-effects deemed due to study medication and sufficiently severe to warrant a change of treatment.

Table 2: Strategies for change in treatment due to side-effects

Clinical Scenario	Strategy
Clear contraindication to a statin	Ineligible
Mild symptoms of myalgia, nausea, dizziness	Temporarily stop study medication. If symptoms improve, restart study medication – subject to investigator’s discretion. If symptoms persist, study medication can be permanently stopped.
Moderate-severe symptoms of abdominal pain or myalgia, with/without biochemical or haematological abnormalities	Temporarily stop study medication. Factors to consider include renal impairment and other medications. On improvement, consider re-challenging with study medication and review. If symptoms persist, study medication can be permanently stopped. If severe reaction, permanently cease study medication and begin appropriate alternate treatment in accordance with local guidelines.

For possible or suspected Statin-Associated Muscle Symptoms (SAMS), the National Prescribing Service (NPS) process will be followed (see Appendix 14).

7.5 Permanent Discontinuation of Study Treatment

Permanent discontinuation of study medication is not considered withdrawal from the study and participants should continue to complete all study assessments in accordance with the intention to treat (ITT) principle. Participants who have temporarily stopped study medication for any reason other than the above should be encouraged to restart study medication as soon as practically, and medically appropriate at the discretion of the investigator.

The investigator must not deviate from the protocol, except when there is a contraindication, due to the participant’s condition or the participant is intolerant of the study medication, in these cases, the study medication should be temporarily stopped. Study medication should also be temporarily or permanently stopped if:

- there is an SAE, which in the opinion of the investigator, is related to the study medication; **and/or**
- the investigator assesses that it is in the participant’s best interest”

8 Concomitant Medications

Investigators are directed to consult the Product Information for atorvastatin for consideration of listed contraindications, special warnings and precautions.

All concomitant medications taken by the participant at screening, baseline and during the study period will be recorded in their study files and entered in the electronic case report form (eCRF). Further instructions about capturing these data will be provided in a procedure manual.

9 Study Withdrawal

If a participant wishes to withdraw or the study team/responsible investigator decides it is in the best interest of the participant to withdraw from further participation in the study, every effort should be made for the participant to report any SAEs to the study team that occur within 4 weeks of their last dose of study medication (as applies), and to attend an end of study visit prior to withdrawal.

10 Co-Enrolment of Participants into Other Studies

Co-enrolment in another investigative drug intervention trial may be considered provided there is agreement between the steering committees of both trials that there are no contraindications or adverse impact on outcomes of either trial. Participants who are enrolled in investigational device, lifestyle trial or observational cohort study, may be included into the STRONGER study at the discretion of the investigator. Co-enrolment of participants into this study is allowed where participants are informed, and there are strategies in place to avoid undue burden on them and/or duplication of research effort through co-operation with other research (trial/s) leaders.

11 Statistical Methods

